7.1.5.3 Calibration of Equipment

The investigator or qualified designee has the responsibility to ensure that any device or instrument used for a clinical evaluation/test during a clinical trial that provides information about inclusion/exclusion criteria and/or safety or efficacy parameters shall be suitably calibrated and/or maintained to ensure that the data obtained is reliable and/or reproducible. Documentation of equipment calibration must be retained as source documentation at the trial site.

See protocol-specified guidance in the Trial Administrative Binder, Procedures Manual, and Site Imaging Manual.

7.1.6 Visit Requirements

Visit requirements are outlined in Section 6.0 - Trial Flow Chart. Specific procedure-related details are provided above in Section 7.1 - Trial Procedures.

7.1.6.1 Screening

Approximately 28 days prior to treatment, potential subjects will be evaluated to determine that they fulfill the entry requirements as set forth in Section 5.1. Screening procedures may be repeated.

Subjects may be rescreened after initially failing to meet the inclusion/exclusion criteria. Results from assessments performed during the initial screening period are acceptable in lieu of repeat screening test if performed within the specified time frame and the inclusion/exclusion criteria is met. Subjects who are rescreened will retain their original screening number. Results of a test performed prior to the subject signing consent as part of routine clinical management are acceptable in lieu of a screening test if performed within the specified time frame.

Screening procedures are to be completed within 28 days prior to the first dose of trial treatment except for the following:

- Laboratory tests and ECOG performance status (PS) are to be performed within 7 days prior to the first dose of trial treatment. An exception is hepatitis testing which may be done up to 28 days prior to the first dose of trial treatment.
- For women of reproductive potential, a urine or serum pregnancy test will be performed within 72 hours prior to the first dose of trial treatment.

7.1.6.2 Treatment Period

Visit requirements are outlined in the Trial Flow Chart (Section 6.0). Specific procedure-related details are provided above in Trial Procedures (Section 7.0).

Subjects who stop study drug with SD or better may be eligible for up to 17 additional trial treatments (approximately 1 year) if they progress after stopping study treatments. Retreatment with study drug is termed the Second Course Phase and is only available if the trial remains open and the subject meets the following conditions:

- **Either**
 - Stopped initial treatment with study treatment after attaining an investigator-determined CR according to RECIST 1.1
 - Was treated with at least 8 trial treatments (approximately 6 months) before discontinuing therapy
 - Received at least two study treatments beyond the date when the initial CR was declared

OR

- Had stable disease (SD), PR or CR and stopped study treatment after 35 treatments (approximately 2 years) for reasons other than disease progression or intolerance

- **AND**
 - Experienced an investigator-determined confirmed radiographic disease progression after stopping their initial study treatment
 - Did not receive any anti-cancer treatment since the last dose of study treatment
 - Has a performance status of 0 or 1 on the ECOG Performance Scale
 - Demonstrates adequate organ function as detailed in Section 5.1.2
 - Female subject of childbearing potential should have a negative serum or urine pregnancy test within 72 hours prior to receiving retreatment with study medication (Cycle 1, Day 1).

- Female subjects of childbearing potential must be willing to use an adequate method of contraception as outlined in Section 5.7.2 – Contraception, starting with the first dose of study medication through at least 120 days or longer based on local regulation, after the last dose of study medication.
 - *Note: Abstinence is acceptable if this is the usual lifestyle and preferred contraception for the subject.*
- Male subjects of child bearing potential must agree to use an adequate method of contraception as outlined in Section 5.7.2 – Contraception, and not to donate sperm starting with the first dose of study therapy through at least 120 days or longer based on local regulation, after the last dose of study therapy.
 - *Note: Abstinence is acceptable if this is the usual lifestyle and preferred contraception for the subject.*
- Does not have a history or current evidence of any condition, therapy, or laboratory abnormality that might interfere with the subject's participation for the full duration of the trial or is not in the best interest of the subject to participate, in the opinion of the treating investigator.

Subjects who enter the Second Course Phase will be retreated with the same treatment as when they last received study treatment. Study treatment will be administered for up to an additional 17 trial treatments (approximately 1 year).

Visit requirements for the second course phase are outlined in the Second Course Phase Trial Flow Chart (Section 6.2).

7.1.6.3 Post-Treatment Visits

7.1.6.3.1 Safety Follow-up Visits

The mandatory Safety Follow-up Visit should be conducted approximately 30 days after the last dose of trial treatment or before the initiation of a new anti-cancer treatment, whichever comes first.

All AEs that occur prior to the Safety Follow-Up Visit should be recorded. Subjects with an AE of Grade >1 will be followed until the resolution of the AE to Grade 0-1 or until the beginning of a new anti-cancer therapy, whichever occurs first. SAEs that occur within 90 days of the end of treatment or before initiation of a new anti-cancer treatment should also be followed and recorded.

Subjects who are eligible for retreatment may have up to two safety follow-up visits, one after the Initial Treatment Period and one after the Second Course Treatment Phase.

7.1.6.3.2 Follow-up Visits

Subjects who discontinue trial treatment for reasons other than disease progression will move into the Follow-up Phase and should be assessed Q12W by radiologic imaging to monitor disease status. Every effort should be made to collect information regarding disease status until the start of a new anti-cancer therapy, disease progression, death, or the end of the study.

Information regarding post-study anti-cancer treatment will be collected if new treatment is initiated.

Subjects who are eligible to receive retreatment according to the criteria in Section 7.1.4.1.4 will move from the Follow-up Phase to the Second Course Phase when they experience disease progression.

7.1.6.3.3 Survival Follow-up

Subjects, who experience disease progression (by site assessment) or start a new anti-cancer therapy, will move into the Survival Follow-Up Phase. Subjects should be contacted (by telephone or visit) approximately every 12 weeks to assess for survival status until death, withdrawal of consent, or the end of the study, whichever occurs first. Post-study anti-cancer therapy will be collected during survival follow-up.

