| • HBsAg, and HBV viral load ^q | | X | X | X | X | X | X | X | X | | X | | | |

| Trial Period: | Screening Phase | Treatment Cycles (3-Week Cycles) | | | | | | | | End of Treatment | Post-Treatment | | | | | | | | | |
|---|-----------------|----------------------------------|----|----|----|----|----|----|----------------|-------------------|------------------------|----------------------------|---------------------------------|--|--|--|--|--|--|--|
| | | 1 | 2 | 3 | 4 | 5 | 6 | 7 | ≥8 | | Safety Follow-up | Follow-up Visits | Survival Follow-up ^a | | | | | | | |
| Treatment Cycle/Title: | Screening | | | | | | | | | At Time of Discon | 30 Days Post Last Dose | Every 12 Weeks Post Discon | Approx. Every 12 Weeks | | | | | | | |
| Scheduling Window (Days) ^b | -28 to -1 | | ±3 | ±3 | ±3 | ±3 | ±3 | ±3 | ±3 | ±3 | ±7 | ±7 | ±7 | | | | | | | |
| • Anti-HBc (total), anti-HBe, anti-HBs, and HBeAg ^q | | | | | | X | | | X | | X | | | | | | | | | |
| Blood for genetic analyses ^t | | X | | | | | | | | | | | | | | | | | | |
| Blood for biomarker studies (serum and plasma) ^o | | X | X | | | X | | | | X | | | | | | | | | | |
| Blood for ctDNA (plasma) ^o | | X | | | | | | | | | | | | | | | | | | |
| Blood for RNA Analysis ^o | | X | X | | | X | | | | X | | | | | | | | | | |
| Tumor tissue for biomarker analysis ^u | X | | | | | | | | | | | | | | | | | | | |
| Efficacy Measurements | | | | | | | | | | | | | | | | | | | | |
| Tumor imaging | X ^v | X ^w | | | | | | | X ^x | | X | | | | | | | | | |
| a. In subjects who experience PD or start a new anti-cancer therapy, contact should be made (by telephone or visit) approximately every 12 weeks to assess for survival status. Updated survival status may be requested by the Sponsor at any time during the course of the study. Upon Sponsor notification, all subjects who do not/will not have a scheduled study visit or study contact during the Sponsor-defined time period will be contacted for their survival status (excluding subjects who have a death event previously recorded). | | | | | | | | | | | | | | | | | | | | |
| b. Cycle 1 treatment must be given within 3 days of randomization. The window for each visit is ±3 days unless otherwise noted. | | | | | | | | | | | | | | | | | | | | |

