7.1.4 Efficacy Measurements

7.1.4.1 Tumor Imaging and Assessment of Disease

The process for image collection and transmission to the blinded central imaging vendor can be found in the Site Imaging Manual (SIM). Tumor imaging should be acquired by computed tomography (CT, strongly preferred). Magnetic resonance imaging (MRI) should be used when CT is contraindicated or for imaging in the brain. However, when MRI is the standard of care at a site, MRI may be used whether or not CT is contraindicated. The same imaging technique regarding modality and use of contrast should be used in a subject throughout the trial to optimize the visualization of existing and new tumor burden.

Expedited confirmation of measurable disease based on RECIST 1.1 by the blinded central imaging vendor at screening will be used to determine subject eligibility. Confirmation of measurable disease by the central imaging vendor per RECIST 1.1 is required prior to subject randomization. Although RECIST 1.1 references a maximum of 5 target lesions in total and 2 per organ, Merck allows a maximum of 10 target lesions in total and 5 per organ.

All scheduled images for all study subjects from the sites will be submitted to the central imaging vendor. In addition, additional imaging (including other modalities) that are obtained at an unscheduled time point to determine disease progression, as well as imaging obtained for other reasons but captures radiologic progression, should be submitted to the central imaging vendor as well.

After the local site investigator-assessed first radiologic evidence of PD, the central imaging vendor will verify PD during the study. Expedited verification of radiologic PD by the central imaging vendor will be communicated to the study site and sponsor.

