7.1.4.1.2 Tumor Imaging During the Trial

The first on-study imaging assessment should be performed at 6 weeks (42 ± 7 days) from the date of randomization. Subsequent tumor imaging should be performed Q6W (42 ± 7 days) or more frequently if clinically indicated. Imaging timing should follow calendar days and should not be adjusted for delays in cycle starts. Imaging should continue to be performed until disease progression is verified by the blinded central imaging vendor (unless site principal investigator [PI] elects to continue treatment and follow irRECIST), the start of new anti-cancer treatment, withdrawal of consent, death, or notification by the Sponsor,

whichever occurs first. All supplemental imaging must be submitted to the central imaging vendor.

Per RECIST 1.1 partial response (PR) and CR should be confirmed by a repeat tumor imaging assessment ≥ 4 weeks from the date the response was first documented. The tumor imaging for confirmation of response may be performed at the earliest 4 weeks after the first indication of response, or at the next scheduled scan (i.e., 6 weeks later), whichever is clinically indicated. Subjects will then return to regular scheduled imaging every 6 weeks, starting with the next scheduled imaging time point. Subjects who obtain a confirmation scan do not need to undergo the next scheduled tumor imaging if it is <4 weeks later; tumor imaging may resume at the subsequent scheduled imaging time point.

Per irRECIST (Section 7.1.4.1.7), disease progression on subjects treated with trial treatment should be confirmed by the site at least 4 weeks after central verification of site-assessed first radiologic evidence of PD in clinically stable subjects. Subjects who have unconfirmed disease progression may continue on treatment at the discretion of the site investigator until progression is confirmed by the site provided they have met the conditions detailed in Section 7.1.4.1.7. Subjects who obtain a confirmation scan do not need to undergo the next scheduled tumor imaging if it is <4 weeks later; tumor imaging may resume at the subsequent scheduled imaging time point if clinically stable. Subjects who have confirmed disease progression as assessed by the site will discontinue the treatment. Exceptions are detailed in Section 7.1.4.1.7.

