7.1.4.1.3 End of Treatment and Follow-up Tumor Imaging

In subjects who discontinue trial treatment, tumor imaging should be performed at the time of treatment discontinuation. If a previous scan was obtained within 4 weeks prior to the date of discontinuation, then a scan at treatment discontinuation is not mandatory. In subjects who discontinue trial treatment due to documented disease progression, this is the final required tumor imaging.

In subjects who discontinue trial treatment without documented disease progression, every effort should be made to continue monitoring their disease status by tumor imaging using the same imaging schedule used while on treatment every 12 weeks (84 ± 7 days) to monitor disease status until (1) the start of new anti-cancer treatment, (2) disease progression, (3) death, or (4) the end of the study, whichever occurs first.

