7.1.4.1.5 RECIST 1.1 Assessment of Disease

RECIST 1.1 will be applied by the blinded central imaging vendor as the primary measure for assessment of tumor response, date of disease progression, and as a basis for all protocol guidelines related to disease status (e.g., discontinuation of study therapy). Initial tumor imaging showing site-assessed PD should be submitted to the central imaging vendor immediately. The site will be notified if the central imaging vendor verifies PD using RECIST 1.1. [Figure 2](#) illustrates the imaging flow involving verification of PD for clinically stable subjects.

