In subjects who have shown initial evidence of radiological PD by RECIST 1.1 as verified by the central imaging vendor, it is at the discretion of the PI whether to continue a subject on study treatment until repeat imaging is obtained (using irRECIST for subject management, see [Table 6](#) and [Figure 2](#)).

This clinical judgment decision by the site investigator should be based on the subject's overall clinical condition, including performance status, clinical symptoms, and laboratory data. Subjects may receive study treatment and tumor assessment should be repeated ≥ 4 weeks later to confirm PD by irRECIST per site assessment. Clinical stability is defined as the following:

- 1) Absence of symptoms and signs indicating clinically significant progression of disease, including worsening of laboratory values,
- 2) No decline in ECOG performance status,
- 3) Absence of rapid progression of disease, and
- 4) Absence of progressive tumor at critical anatomical sites (e.g., cord compression) requiring urgent alternative medical intervention.

Any subject deemed clinically unstable should be discontinued from trial treatment at central verification of site-assessed first radiologic evidence of PD and is not required to have repeat imaging for PD confirmation.

In determining whether or not the tumor burden has increased or decreased per irRECIST, the local site investigator should consider all target and non-target lesions as well as any incremental new lesion(s).

Scenarios where PD is not confirmed at repeat imaging if ALL of the following occur by irRECIST:

- Target lesion sum of diameters is <20% or <5 mm absolute increase compared to nadir,
- Non-target disease resulting in initial PD is qualitatively stable or improved,
- New lesion resulting in initial PD is qualitatively stable or improved,
- No incremental new lesion(s) since last evaluation, and
- No incremental new non-target lesion progression since last evaluation.

If repeat imaging does not confirm PD by irRECIST as assessed by the local site investigator and the subject continues to be clinically stable, treatment may continue and follow the regular imaging schedule.

Scenarios where PD is confirmed at repeat imaging if ANY of the following occur by irRECIST:

- Target lesion sum of diameters remains $\geq 20\%$ and at least 5 mm absolute increase compared to nadir,
- Non-target disease resulting in initial PD is qualitatively worse,

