8.4 Analysis Endpoints

8.4.1 Efficacy Endpoints

8.4.1.1 Primary

Progression-Free Survival (PFS) – RECIST 1.1 by Blinded Central Imaging Vendor Review

PFS is defined as the time from randomization to the first documented disease progression per RECIST 1.1 based on blinded central imaging vendor review or death due to any cause, whichever occurs first. See Section 8.6.1 for definition of censoring.

Overall Survival (OS)

OS is defined as the time from randomization to death due to any cause. Subjects without documented death at the time of the final analysis will be censored at the date of the last follow-up.

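### Section 7.1.6.3.3 starts survival-only follow-up on site-assessed progression, while imaging and primary PFS depend on the central read, so a small group can be informatively censored

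*Combined protocol and SAP*

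**What the plan says.** All references are to the combined protocol and SAP.

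- **Endpoint.** Section 8.4.1.1 measures PFS from randomization to "first documented disease progression per RECIST 1.1 based on blinded central imaging vendor review or death due to any cause".
- **Imaging stop rule.** Section 7.1.4.1.2: "Imaging should continue to be performed until disease progression is verified by the blinded central imaging vendor". It makes an exception where the investigator continues treatment under irRECIST. Its other stopping reasons are new anti-cancer treatment, withdrawal of consent, death and notification by the Sponsor. Progression that only the site has called is not among them.
- **Role of the central read.** Section 7.1.4.1.5 makes the central RECIST 1.1 read the primary measure for response, "date of disease progression, and as a basis for all protocol guidelines related to disease status".
- **Phase change.** Section 7.1.6.3.3: "Subjects, who experience disease progression (by site assessment) or start a new anti-cancer therapy, will move into the Survival Follow-Up Phase". The only activities listed there are survival contact about every 12 weeks and recording of later anti-cancer therapy. As far as the extracted table can be read, flow chart 6.1 marks tumor imaging under Follow-up Visits and not under Survival Follow-up.
- **Assessor not named.** Section 7.1.4.1.3: "In subjects who discontinue trial treatment due to documented disease progression, this is the final required tumor imaging". Flow chart 6.1, footnote a: "In subjects who experience PD or start a new anti-cancer therapy, contact should be made (by telephone or visit) approximately every 12 weeks". Section 7.1.6.3.2 ends follow-up imaging at progression, also without saying whose.
- **Verification.** Section 7.1.4.1: "After the local site investigator-assessed first radiologic evidence of PD, the central imaging vendor will verify PD during the study". The result goes back to the site on an expedited basis.

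**The concern.** Two sections give a site different answers about the same subject. Suppose the site calls progression and the vendor does not verify it. Section 7.1.4.1.2 keeps the subject on scans. Section 7.1.6.3.3 places the subject in a phase with no scans.

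If the site follows the second, no later central progression can be observed. Table 8 censors a subject with no central progression and no death at the last disease assessment. The censoring is then caused by suspected progression, so it is not independent of the endpoint, although the Kaplan-Meier, log-rank and Cox methods in Section 8.6.1.1 assume that it is. PFS is one of two primary endpoints and is tested once, at a one-sided 0.2% level. At stake are lost events and, if the loss differs by arm, a shifted hazard ratio.

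**Working it through.** **1. Who is exposed.** Start with a subject whose site-called progression is not centrally verified.

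- *On treatment and staying on it:* scans continue under Section 7.1.4.1.2. Not exposed.
- *On treatment and clinically unstable:* Section 7.1.4.1.7 says the subject "should be discontinued from trial treatment at central verification of site-assessed first radiologic evidence of PD", so the rule assumes verification has happened. It gives no instruction for the unverified case.
- *Stops treatment anyway:* Section 5.8.1 allows this at any time and for any reason. Exposed.
- *Already off treatment in the Follow-up Phase (Section 7.1.6.3.2):* Table 6 and the treatment rules of Section 7.1.4.1.7 concern continuing treatment and do not apply. Exposed.
- *Starts new anti-cancer therapy first:* Section 7.1.4.1.2 ends imaging and Table 8 censors in any case. The conflict changes nothing.

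**2. What Table 8 does to exposed subjects.**

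- No central progression and no death: censored at the last assessment.
- Later death before new therapy: an event if at most one assessment was missed, censored if two or more consecutive assessments were missed. The plan does not say whether a scan that is no longer scheduled counts as missed, so the fate of these deaths is open.

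**3. The plan's own power figure.** Inputs from Sections 8.9 and 5.3: 331 PFS events, hazard ratio 0.60, one-sided alpha 0.002 (z = 2.878), allocation 2:1 (2/3 × 1/3 = 2/9). By Schoenfeld's formula:

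power = Φ(|ln 0.60| × √(D × 2/9) − 2.878), with |ln 0.60| = 0.5108.

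For D = 331: 0.5108 × √73.56 = 4.381, and 4.381 − 2.878 = 1.503, so power is 93.4%. Sections 8.1 and 8.9 state about 94%, so the figure reproduces. (Table 13 prints 99.00% for the same test. That does not reproduce and is a separate matter.)

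**4. Equal loss in both arms.** The documents give no rate of disagreement between site and central reads, so the loss rates are assumptions.

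| Events lost | D | Power at 0.2% |
|---|---|---|
| 0% | 331 | 93.4% |
| 2% | 324 | 92.7% |
| 5% | 314 | 91.8% |
| 10% | 298 | about 90% |

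The tipping points need no assumed rate. Solving D = ((2.878 + z_power)/0.5108)² × 9/2 gives:

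- 90% power (z = 1.282): D = 298.4, so 331 − 298.4 = 32.6 events lost (9.8%).
- 80% power (z = 0.842): D = 238.6, so 331 − 238.6 = 92.4 events lost (27.9%).

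**5. Unequal loss.** A simulation used six-weekly scans, exponential PFS, 16-month accrual, a Month 22 cut and 10% yearly dropout. Assumed shares of subjects were censored one scan before central progression.

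| Control / pembrolizumab share | Cox HR, true 0.60 | Cox HR, true 1.0 |
|---|---|---|
| 0% / 0% | 0.60 | 1.00 |
| 10% / 10% | 0.60 | 0.99 |
| 20% / 20% | 0.59 | 0.99 |
| 20% / 10% | 0.64 | 1.07 |
| 10% / 20% | 0.55 | 0.94 |

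Equal shares leave the hazard ratio about where it was. Unequal shares move it, in a direction set by which arm loses more. The shares show the mechanism and are not estimates for this trial.

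**The case against.** The best reply is that the text, read as a whole, already gives the answer. Section 7.1.6.3.3 assigns a phase and never says that imaging stops. The opening of Section 7.1.6 sends the reader back to Section 7.1 for procedural detail, which leads to 7.1.4.1.2. Section 7.1.4.1.5 makes the central read the basis for guidelines on disease status, and that could settle the unnamed assessor in 7.1.4.1.3 and footnote a. Verification under Section 7.1.4.1 is not limited to subjects on treatment. Figure 2 and the Site Imaging Manual are not available here and may say more. Figure 2's title limits it to clinically stable subjects.

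This narrows the point but does not remove it. No available text says what happens to imaging when the vendor does not verify, and 7.1.6.3.3 names the site as assessor in a phase with no scans.

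The plan also has three relevant supporting analyses. Sensitivity Analysis 1 counts progression or death despite missed assessments or new therapy. Sensitivity Analysis 2 counts certain treatment discontinuations or new therapy as progression. Investigator-assessed PFS uses the site's own call. They help to reveal the problem. They do not change the primary test, and Sensitivity Analysis 1 cannot recover progression that was never scanned.

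A reader might infer that every site-called progression ends imaging. The documents do not support that: the main on-treatment route runs through central verification. Nor does footnote x of flow chart 6.1, which refers to site-confirmed irRECIST progression, open a second gap, because the note in Section 7.1.4.1.7 requires the first progression to have been centrally verified.

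**Conclusion.** The inconsistency is real and should be corrected, but its reach is limited. It affects subjects with site-called, centrally unverified progression who stop treatment anyway or are already off it, and who have not started new anti-cancer therapy. For them the primary analysis can censor because progression was suspected.

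The size is unknown and probably small. Equal loss costs only power, and about 33 of 331 events would have to go before power fell to 90%. That rests on the Schoenfeld approximation and the plan's hazard ratio of 0.60. A reader might go further and infer a biased hazard ratio or an inflated type I error. The documents do not support either: bias needs loss that differs by arm, double-blinding makes that less likely, and no discordance rate is given.

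Timing matters. PFS is tested once, at about Month 22 (Section 8.7.1). The document history runs from 15-JAN-2016 to 03-FEB-2021, about 60 months, so the test has very probably been done, although the documents do not say so. The 12-week follow-up imaging interval came with the 2021 amendment and is unlikely to have affected it.

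**What to change.** - **Section 7.1.6.3.3:** state that a subject with site-assessed progression not verified centrally stays on endpoint imaging until one of the stopping reasons in Section 7.1.4.1.2 applies. Keep that section's irRECIST exception and its Sponsor-notification clause.
- **Section 7.1.4.1.3 and flow chart 6.1, footnote a:** name the central read as the trigger.
- Treatment decisions are unchanged, and footnote x needs no edit.
- **If PFS has already been analysed:** report, by arm, the number of subjects censored after site progression without central progression. This is then the remedy that still has effect.
- **Minor and separate:** one sentence in Section 7.1.4.1.3 calls for both the on-treatment imaging schedule (six-weekly) and a 12-weekly one. Reconcile the two.

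The cost is wording in two sections and one footnote, with no scan beyond those Section 7.1.4.1.2 already requires. After the analysis, it is one descriptive table.
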